- The de-identified, but self-described, chronic ailments will be used with the scan results to broadly identify cohorts that may benefit from screening for asymptomatic disease.
- What operating cost burden is required to sustain a mobile screening project and what is the minimum utilization required to justify it?
- The operating costs of the study will be captured in order to inform an analysis of the financial constraints for deployment of mobile screening systems into local underserved communities.
- What portion of the asymptomatic patients with advanced disease will be willing to learn about clinical trials?
- Analysis of the posttest behavior of participants by their enrolling to learn more about clinical trials will measure the efficacy of using this method to educate the at risk population about clinical trials and ultimately inform decisions about how trial participants may be recruited in the future.
- What portion of the patients take advantage of free online diet support?
- Lifestyle changes are challenging as it is difficult to engage patients in the weeks following any testing. Tracking of the number who take advantage of the follow-up support will help guide future efforts to develop educational materials.

Patient Selection Criteria

The screening will be available to adults who self-select and who meet the inclusion criteria. The project will stop at 3 months or 1,000 patients, whichever occurs first. The goal is to

examine whether a self-referral design can serve as a cost effective patient centered wellness screening model.

Who may participate

- Adults 18 and over
- Patients with no diagnosis of liver disease
- Patients with any of these self-identified chronic conditions
 - Type 2 diabetes
 - Metabolic syndrome
 - Cardiovascular disease
 - Pre Diabetes
 - Sleep apnea
 - Digestive disorders
 - Osteoporosis
 - Polycystic ovarian syndrome
 - Psoriasis

Who may not participate

- Age less than 18
- Pregnant women
- Anyone with an implanted electronic device such as a defibrillator
- Morbidly obese, BMI 40 or greater
- Anyone not personally able to give informed consent
 - Non English speakers, no translator is available

Trial Candidate Outreach

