 - The discussion provided useful information about FDA-approved clinical trials of therapies.
 - The discussion of my liver health will help me obtain better health care for my liver.
- b. If you answered dissatisfied or very dissatisfied, please check all the reasons for your answer:
- I do not understand what the CAP-FibroScan measures.
 - I do not understand how much fat I have within my liver.
 - I am not sure if I have or do not have scarring (fibrosis) of my liver.
 - The results did not give me a better understanding of my liver health.
 - The discussion did provide useful information about FDA-approved clinical trials of therapies.
 - The discussion of my liver health is unlikely to help me obtain better health care for my liver.

SUNN STUDY

STATISTICAL ANALYSIS PLAN

PRIMARY OUTCOME MEASURE – DETERMINE THE INCIDENCE AND STAGING OF UNDIAGNOSED NAFLD AND NASH IN A HEALTH CONSCIOUS SELF SELECTED POPULATION AS MEASURED WITH A FIBROSCAN

The study will measure the incidence and severity of the fat content and liver stiffness in an at large, self selected population who do not, at the time of testing, have a diagnosis of NAFLD, NASH or other liver disease. This will measure the incidence of undiagnosed liver disease and the statistical distribution of the disease staging in this population.

A key secondary outcome measure will be the incidence and disease distribution as a function of ethnicity.

We will analyze data using a standard statistical software package, Stata® 12.1 (Stata Corp, College Station, TX). We will express continuous variables using the mean \pm standard deviation, and we will test the null-hypothesis using the Student t-test. We will compare categorical variables using contingency table analysis. For all statistical tests, we will define a two-sided p-value of ≤ 0.05 as statistically significant. We will perform multivariate analysis of all risk factors found to be statically significant ($p \leq 0.05$) using univariate analysis.

Data Analysis

We will record all data in a Microsoft Excel worksheet. We will sequentially number each participating subject. We will not record any identifying information (e.g., names, initials, DOB, SSN, insurance, EPIC MRNs) in the database. Thus, all data assessments will maintain the anonymity of all participating subjects.

1. The primary goal is to calculate the proportion of men and women that when tested have CAP-FibroScan evidence of:
 - No fat or liver stiffness

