 - No fat but evidence of liver stiffness
 - Fat without liver stiffness
 - Fat with liver stiffness
 - Stiffness values indicative of cirrhosis
 - Stiffness values indicative of fibrosis without cirrhosis

NOTE: no individual follow up or track will be done as not personally identifiable information will be captured or retained.

2. The secondary goal is to determine factors that are statistically significantly associated with the presence or absence of fat with or without increased liver stiffness.

We will analyze data using a standard statistical software package, Stata® 12.1 (Stata Corp, College Station, TX). We will express continuous variables using the mean ± standard deviation, and we will test the null-hypothesis using the Student t-test. We will compare categorical variables using contingency table analysis. For all statistical tests, we will define a two-sided p-value of ≤0.05 as statistically significant. We will perform multivariate analysis of all risk factors found to be statically significant (p ≤0.05) using univariate analysis.

This exploratory goal seeks to determine the degree of satisfaction of subjects who undergo a screening CAP-FibroScan free of charge.

We will calculate the frequency of answers for each of the five items reflecting subjects' likelihood of:

- recommending this test to a friend or family member.
- sharing their results with their doctor.
- consulting with a liver specialist.
- seeking information about FDA-approved clinical trials of therapies for non-alcoholic fatty liver disease.
-

We will not perform statistical analyses for these descriptive data.

Disease Staging

The disease staging to be analyzed will be based upon these breakpoints from the FibroScan test. The test scores will be translated into these staging ranges for analysis.

Transient Elastography (TE):

Disease	F0-F1	F2	F3	F4
NAFLD/NASH	≤ 7.0	≤ 7.5	≤ 10.0	≤ 14.0

Reference: Current Gastroenterology Reports. 2014; 16: 372

TE Interpretation: The subject's liver stiffness score in kPa units shows:

- **F0:** No liver fibrosis
- **F1-2:** Mild-Moderate liver fibrosis
- **F3:** Severe liver fibrosis
- **F4:** Cirrhosis

Controlled Attenuation Parameter:

Steatosis Grade	% Steatosis on Liver Biopsy	CAP Value
Mild (S1)	5-33%	225-275 dB/M
Moderate (S2) to Severe (S3)	>33% >66%	275-400 dB/M

Reference: World J Gastroenterol. 2016; 22: 7236

DATA COLLECTION

Demographics:

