The data for analysis will be captured by these patient completed forms to provide demographic information, including sex, age, and race/ethnicity. We will measure height and weight prior to CAP/FibroScan testing.

Metabolic Syndrome:

Subjects will use a form to check YES or NO for comorbid components of the metabolic syndrome that they may or may not have:

- Obesity/overweight
- Diabetes mellitus
- Hypertension
- Hypercholesterolemia
- Hypertriglyceridemia
- Gout or elevated uric acid

Other Health Conditions:

Subjects will use a form to check YES or NO for other health conditions they may or may not have:

- Heart disease
- Heart attack
- Arrhythmia
- Stroke
- Arthritis
- Osteopenia/osteoporosis
- Hypothyroidism
- Low Vitamin D
- Low testosterone
- Menopausal state
- Inflammatory bowel disease (ulcerative colitis or Crohn's disease)
- Cancer
 - Skin: melanoma
 - Skin: basal cell or squamous cell cancers

- Other type of cancers: lymphoma; leukemia; head or neck; thyroid; brain; breast; lung; stomach; colon; liver; ovary; uterus; prostate; bone

Diet:

Subjects will fill out a form using a 5-point scale of the frequency of their average weekly dietary intake of specific food types: (A. 0 days, B. 1-2 days, C. 3-4 days, D. 5-6 days, E. 7 days per week)

- Proteins: eggs, cheese, beans, fish, chicken, turkey, beef, pork
- Starchy carbohydrates: breads, rolls, pasta, cereals, potatoes, rice, corn, peas, lima beans
- Non-starchy vegetables: lettuces, kale, carrots, green beans, broccoli, peppers, onions, cucumber
- Fats: butter, margarine, avocado, oils (olive, safflower, cottonseed, peanut, sesame, walnut)
- Nuts: peanuts, walnuts, cashews, almonds, macadamias, peanuts
- Sugars or Syrups: sugar, high fructose corn syrup (sodas), maple or corn syrups
- Fast food meals
- Eating out at restaurants

Exercise:

Subjects will fill out a form using a 5-point scale of the frequency of their average weekly exercise:

- (A. 0 days, B. 1-2 days, C. 3-4 days, D. 5-6 days, E. 7 days per week)
- Cardiovascular: brisk walking, jogging, biking, treadmill, stationary bike, stair stepper, elliptical, swimming laps
 - Strength: weight lifting, resistance machines or cords

Alcohol:

Subjects will fill out a form quantifying their average weekly total of alcoholic drinks:

(1 drink= 12 oz. beer, 6 oz. wine, 1.5 oz. hard liquor; 3 oz. brandy, sherry, liqueur):

- None
- 1-2 drinks/week
- 3-4 drinks/week
- 5-6 drinks/week
- 7-8 drinks/week
- 9-10 drinks/week

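### The ethnicity outcome has no analysis of its own: the crude contingency table can create or hide a difference, and the screened multivariate step does not guarantee age and sex adjustment

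*Combined protocol and SAP*

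**What the plan says.** Under Primary Outcome Measure, the SAP gives the outcome: "A key secondary outcome measure will be the incidence and disease distribution as a function of ethnicity". One general methods paragraph follows. For a categorical factor against a categorical result it says "We will compare categorical variables using contingency table analysis", with significance at a two-sided 0.05. It ends: "We will perform multivariate analysis of all risk factors found to be statically significant", where the threshold is again univariate p ≤ 0.05.

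The Data Analysis section repeats that paragraph under a different aim: "The secondary goal is to determine factors that are statistically significantly associated with the presence or absence of fat with or without increased liver stiffness". No model type, outcome coding or compulsory covariate is named in either place. The primary proportions are planned separately for men and women; no such split is stated for ethnicity.

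The data needed for adjustment will exist, because the forms collect "demographic information, including sex, age, and race/ethnicity" (Data Collection, Demographics). On sampling, Patient Selection Criteria says "The screening will be available to adults who self-select and who meet the inclusion criteria". Trial Candidate Outreach lists physician referral, social media, internet advertising, online forums and support groups. There are no quotas by age, sex or ethnicity.

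**The concern.** With open volunteering, nothing makes the ethnic groups alike in age or sex. If one group's volunteers are older, and stiffness or fat rises with age, a crude table shows an ethnic difference even when none exists at a given age. If the group with the higher age-specific risk happens to be younger, the table can hide a real difference.

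This matters because the outcome is labelled key secondary and is open to a significance test. The protocol also wants the data to identify groups that may benefit from screening and to support a change in guidance. A difference produced by who volunteered, or a real one missed, would misdirect both uses.

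**Working it through.** **The plan's own figures.** The protocol (Intended Use of the Data) gives a minimum of 400 participants, a maximum of 1,000, and power of around 0.8. It states no effect size, SD or rate, and no figure for ethnicity, so there is nothing to reproduce for this outcome. The calculations below use totals of 400 and 1,000; every other input is an assumption.

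**False difference.** Assume two ethnic groups, two age strata (under 50, and 50 or over), stage F2 or above in 5% and 15% of the strata, and no ethnic effect within a stratum. If a share s of a group is older, its crude rate is 0.05(1 − s) + 0.15s = 0.05 + 0.10s.

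- Older share 45% v 55%: 9.5% v 10.5%, a false gap of 1 point.
- 40% v 60%: 9% v 11%, a gap of 2 points.
- 30% v 70%: 8% v 12%, a gap of 4 points.

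Hand check for 30/70 with 200 + 200. The pooled rate is 10%, so the null SE is √(0.10 × 0.90 × 2/200) = 0.0300 and the critical gap is 1.96 × 0.0300 = 0.0588. The actual SE is √[(0.08 × 0.92 + 0.12 × 0.88)/200] = 0.0299. The upper-tail chance of p ≤ 0.05 is 1 − Φ[(0.0588 − 0.04)/0.0299] = 1 − Φ(0.63) ≈ 0.26.

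Simulated chance that ethnicity is declared significant (the three crude figures are for 200 + 200, 500 + 500 and 800 + 200):

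| Older share | Crude test | Age-stratified Mantel-Haenszel | Univariate screen, then logistic model |
|---|---|---|---|
| 45/55 | 6%, 8%, 8% | 5% | 3–4% |
| 40/60 | 10%, 18%, 15% | 5% | 2–3% |
| 30/70 | 26%, 55–56%, 43–44% | 5% | 2–3% |

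The last column applies the SAP's sequence to ethnicity. It works here because the age effect that biases the crude table also carries age through the screen: age fails in about 7% of runs at 400 and in 0.1% or fewer at 1,000.

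**When age may not pass.** Take 400 participants, older shares 40/70, and either rates of 30%/40% with equal groups or 5%/10% with a 20% minority. Age then fails the screen in 46–52% of runs. A false crude result stands without age adjustment in 2.5–3.4% of all runs. The total false-positive rate of the screened sequence is still only 4–5%, so the loss is assurance of adjustment rather than gross inflation.

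**Masking.** Take 1,000 participants with a 20% minority that is younger (40% older, against 70% in the majority). Majority rates are 20% younger and 40% older; the minority is 10 points higher in each stratum.

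- Majority crude rate: 0.3 × 0.20 + 0.7 × 0.40 = 34%.
- Minority crude rate: 0.6 × 0.30 + 0.4 × 0.50 = 38%.
- The 10-point excess shows as 4 points; the age mix hides 0.30 × 20 = 6.

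Hand check: the pooled rate is 34.8%, the null SE is √[0.348 × 0.652 × (1/800 + 1/200)] = 0.0377 and the critical gap is 0.0738. The actual SE is 0.0382, so power is about 1 − Φ[(0.0738 − 0.04)/0.0382] = 1 − Φ(0.88) ≈ 0.19. Simulation gives 19% for the crude test and 76% with age included. Under the screening rule ethnicity fails to reach the model in 100 − 19 = 81% of runs, so the later step cannot recover it.

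**The case against.** The strongest reply is that adjustment is already planned, in the same paragraph as the contingency table. A reader might infer that the ethnicity result will be reported crude only, and that 26–56% is the plan's false-positive rate. The documents do not support either inference. On a plain reading, a significant ethnic difference can go on to the multivariate analysis, and if it does, about 2–4% of false positives remain in the main scenarios.

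A reader might also infer that age and sex differences will appear as ethnic differences. That goes too far as well. Confounding needs the groups to differ in age or sex, and needs those factors to relate to disease; the documents give no figure for either. With a 10-point age gap the crude test is close to nominal. Confounding by sex was not calculated.

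Finally, crude proportions are a legitimate description of those who come forward. Intended Use of the Data presents breakdowns by population as leads for later work, and no causal ethnic claim is made. That stands, and it is why the crude figures should stay.

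What the reply does not meet is this. The multivariate sentence is nowhere linked to the ethnicity outcome, it does not require age and sex, and it admits only factors already significant on their own. That last rule is what makes masking irreparable.

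**Conclusion.** The point holds as a weakness in the specified analysis, not as a demonstration that the ethnicity result will be wrong. The SAP names a key secondary outcome, offers an unadjusted test for it, and leaves adjustment to a screen that may omit age, sex or ethnicity itself. False positives are a real risk if the crude p-value is what gets reported: from 6–8% to 26–56% over the assumed age gaps of 10 to 40 points. They are mostly removed if the screened model is applied to ethnicity. The firmer problem is masking, with detection of 19% against 76% in the single scenario examined. All these sizes rest on assumed age mixes and disease rates, two ethnic groups and two age strata. They show what can happen, not what this sample will show. Cheap improvement.

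**What to change.** In the SAP, give the ethnicity outcome its own paragraph:

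- Report crude proportions by ethnicity, labelled as a description of the volunteers.
- Beside them, report proportions directly standardised to the pooled study age-sex distribution, with confidence intervals.
- Base the ethnicity p-value on a comparison that always includes age and sex, whatever their univariate p-values or that of ethnicity: a stratified Mantel-Haenszel test, or a logistic model for presence and an ordinal model for stage.
- Put BMI and diabetes in a separate, labelled model, since they may lie on the pathway from ethnicity to disease.
- Name the ethnic categories and the reference group.
- State that adjustment does not remove other self-selection, such as motivation or referral route.

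The cost is SAP wording and a few lines of code; age, sex and ethnicity are already on the form. The one downside is slightly wider intervals in small ethnic groups.

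### The Student t-test is the only test named for continuous variables; between groups of unequal size it misses its 5% level if the SDs also differ, and no test is named for three or more groups

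*Combined protocol and SAP*

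**What the plan says.** The same analysis paragraph appears twice in the SAP, under Primary Outcome Measure and under Data Analysis, item 2. On summaries it says "We will express continuous variables using the mean ± standard deviation", and on testing "we will test the null-hypothesis using the Student t-test". For categorical data it says "We will compare categorical variables using contingency table analysis". The threshold is common to all: "For all statistical tests, we will define a two-sided p-value of ≤0.05 as statistically significant". The univariate results then select the model: "We will perform multivariate analysis of all risk factors found to be statically significant", again at p ≤0.05.

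Item 2 looks for "factors that are statistically significantly associated with the presence or absence of fat with or without increased liver stiffness". Fat (yes/no) crossed with stiffness (yes/no) gives up to four groups. The SAP also states: "A key secondary outcome measure will be the incidence and disease distribution as a function of ethnicity". On stage, the Disease Staging section says "The test scores will be translated into these staging ranges for analysis".

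The documents name no unequal-variance test, rank test, transformation or analysis of variance. They do not say which form of the t-test is meant; without qualification, the pooled-variance form is the usual reading.

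**The concern.** The pooled t-test assumes that both groups have the same variance. A large sample protects it against non-normality, but not against unequal variances combined with unequal group sizes. Participants here select themselves, and nothing in the plan balances the disease groups or the ethnic groups, so unequal sizes are likely. Whether the variances differ is unknown.

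At stake is the screening step. A continuous factor enters the multivariate model if its univariate p is ≤0.05. If the smaller group is the more variable, the test rejects too often. If it is the less variable, the test rejects too seldom, and a real difference in means may be dropped. A second gap is that a t-test compares two groups, while item 2 can produce four and no method is given for a continuous variable across them.

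**Working it through.** **Inputs from the documents.** Two-sided 0.05 for every test (SAP); at least 400 and at most 1,000 participants (protocol, Intended Use of the Data). Group sizes, SDs and effect sizes are not given.

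**The plan's own figure.** The plan gives no error rate for the t-test. Its nearest figure is power of around 0.8 with 400 participants. With no effect size, SD or group split stated, this can be neither reproduced nor refuted. For orientation, the standardized difference detectable with 80% power is (1.960 + 0.842) × √(1/n1 + 1/n2): 0.28 at 200 v 200 and 0.47 at 40 v 360.

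**Assumptions.** Smaller group n1 = 40, larger group n2 = 360. The larger group's SD is 1, the smaller group's is r, and the means are equal.

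**Formulas.**
- True variance of the mean difference: V_true = r²/n1 + 1/n2
- Variance the pooled test uses: V_pool = [((n1−1)r² + (n2−1)) / (n1+n2−2)] × (1/n1 + 1/n2)
- Large-sample error rate: 2 × [1 − Φ(1.960 × √(V_pool/V_true))]

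**Worked case, r = 1.5.** V_true = 2.25/40 + 1/360 = 0.0590. V_pool = [(39 × 2.25 + 359)/398] × 0.02778 = 1.1225 × 0.02778 = 0.0312. The ratio is 0.528 and its root 0.727, so the effective critical value is 1.960 × 0.727 = 1.424 and the error is 15.4%.

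| SD ratio r | V_pool/V_true | Error, 40 v 360 | Error, 100 v 900 |
|---|---|---|---|
| 0.67 | 1.877 | 0.7% | 0.7% |
| 1 | 1.000 | 5.0% | 5.0% |
| 1.1 | 0.858 | 6.9% | 6.9% |
| 1.25 | 0.700 | 10.1% | 10.1% |
| 1.5 | 0.528 | 15.4% | 15.4% |
| 2 | 0.350 | 24.6% | 24.6% |

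The V_pool/V_true column is for 40 v 360. The last column has the maximum N with the same shares: a larger sample does not help.

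**Check by simulation** (20,000 normal datasets per setting, 40 v 360). The pooled test gave 4.9%, 15.4% and 24.7% at r = 1, 1.5 and 2; Welch's test gave 4.9% to 5.0%. With 200 v 200, both tests stayed at about 5% at every ratio tried.

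**Other splits, r = 1.5 to 2.** The pooled error was 10.7% to 15.2% at 100 v 300 and 17.0% to 28.5% at 20 v 380.

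**Limits of Welch.** With log-normal data (log-SD 0.5), Welch ran at 6.0% to 6.9% with a smaller group of 20 and 6.9% to 7.7% with a smaller group of 12. In those data with equal SDs, the pooled test held 4.9% and 4.6%.

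**The case against.** The strongest case on the other side is about reach, and most of it stands.

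- **The main results are not affected.** A reader might infer that the primary outcome or the key secondary outcome is at risk. The primary outcome is a set of proportions. Incidence by ethnicity is a proportion, and stage is analysed in ranges. Contingency tables cover these for any number of groups.
- **Few factors are continuous.** Sex, ethnicity, the yes/no conditions and the banded diet, exercise and alcohol answers are categorical as collected. Only age, height and weight (hence BMI) are continuous candidates. In item 2, kPa and dB/m define the outcome and are not candidate factors, so skewness of kPa has no bearing on the screening step.
- **A plainly irrelevant factor is not let in.** A factor fully independent of disease has the same SD in every disease group, and the pooled test then holds its level. With equal SDs, the simulated error was 4.6% to 5.3%, even for 12 v 388 with skewed data. The inflated rates apply to a factor whose mean is equal across groups but whose spread is not.
- **Unequal SDs are assumed.** Nothing in the documents shows them. BMI is capped below 40 by the exclusion criteria, and a mild ratio of 1.1 gives only 6.9%.
- **Pairwise testing is not planned.** A reader might infer that ethnic groups will be compared by all pairwise t-tests, with the multiplicity that follows. The SAP states no such procedure. What it shows is a gap: no method for a continuous variable across three or more groups.

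The objection does not remove the point for the few continuous variables. Unequal group sizes are likely, equal variances are not assured, and a larger N gives no protection.

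**Conclusion.** The point holds in a limited form. For age, height, weight and BMI, and for raw kPa or dB/m if they are also analysed, the pooled t-test misses its 5% level when group sizes and SDs both differ. At an assumed 40 v 360, the error runs from about 0.7% (SD ratio 0.67) to about 25% (SD ratio 2). These figures depend on a split and on SD ratios that the documents do not give. A small group alone does no harm. It would be wrong to conclude that the study's screening is known to be distorted or that its primary results are in doubt. The improvement is cheap and of modest importance.

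**What to change.** In both places where the analysis paragraph appears:

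1. Replace the Student t-test with Welch's unequal-variance t-test for comparisons of two groups.
2. For a continuous variable across three or more groups, such as the four fat-by-stiffness groups, name one global test that allows unequal variances, to be done before any pairwise comparison. Either Welch's analysis of variance or regression on group with robust standard errors and a joint test would serve.
3. If raw kPa is analysed and proves skewed, report the median and interquartile range as well as the mean ± SD.

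The cost is SAP wording; no data collection changes. If the variances are in fact equal, Welch uses fewer degrees of freedom. At 40 v 360 they are (1/40 + 1/360)² / [(1/40)²/39 + (1/360)²/359] ≈ 48 instead of 398, which moves the critical value only from 1.97 to 2.01. With very small, skewed groups of 12 to 20, Welch can still run at about 6-8%, so p-values from such groups should be read with caution.

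### The SAP names no method that uses the order of its 11 ordered diet, exercise and alcohol items; if an unordered chi-square is used near N = 400, a linear gradient can lose about 20 points of power (about 35 for alcohol)

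*Combined protocol and SAP*

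**What the plan says.** The SAP's Data Analysis section, item 2, sets the aim: "The secondary goal is to determine factors that are statistically significantly associated with the presence or absence of fat with or without increased liver stiffness". Two univariate methods follow, in the same words as under Primary Outcome Measure. For continuous variables, "we will test the null-hypothesis using the Student t-test"; for the rest, "We will compare categorical variables using contingency table analysis". The threshold is common to all tests: "we will define a two-sided p-value of ≤0.05 as statistically significant". It also controls entry to the model: "We will perform multivariate analysis of all risk factors found to be statically significant (p ≤0.05) using univariate analysis".

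The SAP's Data Collection section defines the lifestyle factors:

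- **Diet:** "Subjects will fill out a form using a 5-point scale of the frequency of their average weekly dietary intake of specific food types". Eight food or meal types are listed, each with five levels from 0 to 7 days per week.
- **Exercise:** "Subjects will fill out a form using a 5-point scale of the frequency of their average weekly exercise". There are two items, cardiovascular and strength, with the same five levels.
- **Alcohol:** "Subjects will fill out a form quantifying their average weekly total of alcoholic drinks". There are ten bands, from none to 21 or more drinks per week.

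That makes 8 + 2 + 1 = 11 ordered factors. The SAP does not say whether they count as continuous or categorical, which contingency-table test is meant, or what scores the levels would carry.

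**The concern.** The 11 items are recorded as tick-box categories, so the natural reading sends them to the contingency table, where the usual test is Pearson's chi-square. That test gives the same result however the levels are shuffled. Against a binary outcome it spreads a steady gradient over 4 degrees of freedom for five levels, or 9 for ten bands, when one would do.

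The secondary goal is at stake. The protocol's Overview names diet and lifestyle as the main drivers of the disease, so these items are among the more plausible modifiable factors. A real gradient that narrowly misses p ≤0.05 because of an inefficient test is lost twice: it is not reported as associated, and it does not reach the multivariable model. Leaving the test open also lets the analyst choose between an unordered test, a trend test and a t-test on scores after seeing the data, and that choice can decide which factors pass.

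**Working it through.** **The plan's own figure.** The protocol, under Intended Use of the Data, gives at least 400 participants for power of about 0.8, with a maximum of 1,000. It states no effect size, standard deviation or prevalence, so the figure can be neither reproduced nor refuted. At two-sided 0.05 and N = 400, power of 0.8 would correspond, for example, to a standardised difference of 0.28 (200 versus 200), a correlation of 0.14, or 10% versus 20% (200 versus 200). I use 80% at N = 400 only as a benchmark for the trend test.

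**Inputs.** From the documents: alpha 0.05 two-sided; 5 or 10 levels; N from 400 to 1,000. Assumed: a binary outcome, a linear gradient in the scores, and an unordered Pearson test as the comparator.

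**Step 1: same signal, different degrees of freedom.** Power = P[χ²(df, λ) > χ²(0.95, df)], where λ is the noncentrality. Under a linear gradient λ is the same for both tests. A 1-df test has 80% power at λ = 7.849. With the same effect, λ grows with N, so at N = 1,000 it is 7.849 × 1,000/400 = 19.62.

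| Test | Critical value | Power, N = 400 | Power, N = 1,000 |
|---|---|---|---|
| Trend, 1 df | 3.841 | 80.0% | 99.3% |
| Unordered, 5 levels, 4 df | 9.488 | 59.5% | 96.1% |
| Unordered, 10 bands, 9 df | 16.919 | 44.6% | 89.6% |

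The loss at N = 400 is 80.0 − 59.5 = 20.5 points for a five-level item and 80.0 − 44.6 = 35.4 for alcohol. At N = 1,000 it is 99.3 − 96.1 = 3.2 and 99.3 − 89.6 = 9.7.

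**Step 2: sample size needed to recover 80%.** The unordered test needs λ = 11.935 on 4 df and 15.650 on 9 df. The ratios are 11.935/7.849 = 1.52 and 15.650/7.849 = 1.99, so 400 becomes 609 and 798.

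**Step 3: dependence on the benchmark.** Loss in points for other levels of trend-test power:

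| Trend power | 50% | 70% | 80% | 90% | 95% | 99% |
|---|---|---|---|---|---|---|
| 4 df | 19.2 | 21.8 | 20.5 | 16.0 | 11.3 | 4.2 |
| 9 df | 28.3 | 35.1 | 35.4 | 31.0 | 24.6 | 11.9 |

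**Step 4: simulation at N = 400.** Outcome prevalence was set at 10%, 30% and 50%, with trend power tuned to about 80%. Five-level items lost 20.7 to 21.7 points and ten evenly filled bands lost 35.9 to 37.0. An assumed skewed alcohol distribution (35% in the lowest band, 1.5% in the highest) lost 15.8, 29.5 and 38.6 points at the three prevalences. The smallest of these needs care. At 10% prevalence the top band expects 400 × 0.015 × 0.10 = 0.6 cases, where the chi-square approximation is poor.

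**Step 5: a non-monotone shape.** Under a symmetric U-shape (N = 400, prevalence 30%) the trend test had 6% to 8% power and the unordered test 32% to 99.8%. The advantage reverses.

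**The case against.** A reader might infer that the SAP commits to ignoring the order, at a cost of 20 to 35 points across all 11 factors. The documents do not support that reading, for these reasons:

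- Contingency-table analysis is a family of methods. Cochran-Armitage and linear-by-linear tests belong to it, so the SAP's wording does not exclude them. The gap is an unnamed test, not a stated wrong one.
- The items could be scored and given the t-test. With a binary outcome this is almost the trend test: trend χ² = N·r² and t² = (N − 2)·r²/(1 − r²). With N·r² = 7.849 at N = 400, t² = 398 × 0.01962/0.98038 = 7.97. On that reading nothing is lost.
- The figure of about 35 points belongs to alcohol alone; the other ten items lose about 20 each. Both rest on a linear gradient and enrolment near the minimum.
- The documents do not establish monotone effects. Several food groups are mixed: the fats item, for instance, combines butter with olive oil.
- The primary goal is a set of proportions, and the SAP's key secondary outcome concerns ethnicity. These items serve only the risk-factor goal.

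All of this stands and narrows the point, but does not remove it. Items collected as categories go by default to an unordered chi-square, and nothing in the SAP directs the analyst elsewhere. The maximum of 1,000 is a cap: under Patient Selection Criteria, enrolment ends at 3 months if that comes first. The entry rule has weaknesses of its own, which are a separate matter; here it only carries a univariate miss forward.

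**Conclusion.** The point holds as a gap in specification with a conditional cost. The SAP names no method that uses the order of the ten five-level items and the ten-band alcohol item. With an unordered chi-square, a binary outcome and a linear gradient at 80% trend power, N = 400 gives about 60% power per five-level item and about 45% for alcohol. The cost shrinks to about 3 and 10 points for the same effect at N = 1,000, vanishes if the items are scored and analysed with a 1-df test, and reverses for a symmetric U-shape. It bears on the secondary risk-factor goal and on which factors enter the multivariable model. It should be corrected, but it does not threaten the main results.

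**What to change.** Add to the SAP, Data Analysis item 2:

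- For each binary fat or stiffness outcome, test the 11 ordered items with a prespecified 1-df trend test (Cochran-Armitage or linear-by-linear).
- State the scores in advance, either equally spaced ranks or fixed values. Band midpoints alone are not enough, because the top alcohol band, 21 or more, has none; give it a stated score.
- Enter each item in the multivariable model as a single ordered score.
- Keep the unordered table as a check for non-monotone patterns.

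On the form, make the alcohol bands non-overlapping. At present 10 drinks fits both 9-10 and 10-12, and 14 drinks fits both 13-14 and 14-20. If forms have already been completed, merging each overlapping pair leaves 10 − 2 = 8 clean bands.

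The cost is a few SAP sentences and a small form correction, with no extra participants or measurements. The drawback is lower power for purely U-shaped relations, which is why the unordered table stays.
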